### 7.1.1 Pre-screening (Visit 0)

A pre-screening visit will be carried out 2 to 7 days before screening, in order to fully explain the study to the subject by the Investigator or his/her designee. The Investigator or his/her designee should provide subject ample time and opportunity to inquire about details of the trial and to decide whether or not to participate in the trial.

If subject agrees to participate, the signed and dated informed consent must be obtained before any study related procedures.

The following procedures will take place at pre-screening:

- Concomitant medications: any medication taken regularly at the time of the ICF signature will be recorded.
- The subject will be informed about the study restrictions and the wash outs to be respected prior to screening visit.
- ACQ5 questionnaire can be performed at this visit or at the following one.

If the study restrictions and wash-out requirements (see [Section 7.2](#)) are respected at Visit 0, Visit 0 and Visit 1 can be combined in one visit.

### 7.1.2 Screening (Visit 1)

A screening visit will be carried out in order to confirm a subject's eligibility for the study.

|  |                      |
|--|----------------------|
| Clinical Study Code No.: CLI-05993AB6-07 | Version No.: 2.0     |
| EUDRACT No.: 2022-000536-36              | Date: 30 August 2022 |

The visit will take place 2 to 7 days after the pre-screening visit, and 2 to 21 days before TP1 (i.e. randomisation and administration of the first study treatment). In case the restrictions are not respected the visit can be rescheduled once

The following procedures will take place at screening:

- Demographic data collection: demographic data including age, gender and race will be recorded;
- Physical examination: a comprehensive physical examination will be performed;
- Medical/surgical history, concomitant diseases and previous medications: subject's medical and surgical history, as well as concomitant diseases (i.e. diseases pre-existing at the time of the ICF signature) will be recorded. Any medications taken in the month preceding the pre-screening visit will be recorded;
- Study restrictions: study restriction criteria will be checked according to [Section 7.2](#);
- Concomitant medications: any medication taken regularly at the time of this visit will be recorded;
- AE recording: the occurrence of any AEs since the pre-screening visit (ICF signature) will be checked, AEs will be recorded in the eCRF, along with the related concomitant medications.

In cases where CS abnormalities are revealed during the physical examination or screening procedures, these will be recorded in the subject's eCRF as medical history, unless the start date/time is after the ICF signature date/time and it is not due to a pre-existing condition. In the latter case, it will be recorded in the eCRF as an AE;

- Local safety ECG: triplicate 12-lead ECG will be used to measure heart rate (HR), QRS interval (QRS), PR interval (PR) and QT interval corrected using Fridericia's formula (QTcF). The assessment will be performed according to [Section 7.3.3](#);
- Blood pressure: SBP and DBP will be measured according to [Section 7.3.2](#);
- Blood test: blood samples will be collected for safety evaluations (clinical chemistry and haematology), after the 12-lead ECG and blood pressure assessments, according to [Section 7.3.4](#);
- FSH or pregnancy tests: blood samples will be collected from female subjects for FSH (for not childbearing potential women) and serum pregnancy tests (for childbearing potential women), according to [Section 7.3.4](#);
- Urine test: urine samples will be collected for urinalysis, according to [Section 7.3.5](#);
- Height and weight: will be recorded;
- Lung function: single spirometry will be performed (after the ECG records and the assessment of the Vital signs) according to [Section 7.3.1](#);
- Bronchodilator reversibility or bronchial challenge test: will be performed in case documented evidence of excessive variability in lung function is not provided, or in case the documentation is older than 2 years;
- Asthma Control Questionnaire® (ACQ-5): asthma control level will be assessed using the ACQ-5 questionnaire, according to [Section 7.3.6.1](#);
- Training: subjects will receive training on the proper use of the inhaler with a pMDI placebo, according to [Section 6.2.4.1](#);
- Subject selection: inclusion/exclusion criteria will be checked (see [Section 4.2](#) and [Section 4.3](#), respectively).

|  |                      |
|--|----------------------|
| Clinical Study Code No.: CLI-05993AB6-07 | Version No.: 2.0     |
| EUDRACT No.: 2022-000536-36              | Date: 30 August 2022 |

### 7.1.3 Treatment Period 1 (TP1)

TP1 is the first visit of the investigational phase and takes place 2 to 21 days after screening.

The following procedures and assessments will take place during this ambulatory visit:

- Subject selection: inclusion and exclusion criteria will be re-checked (see [Section 4.2](#) and [Section 4.3](#), respectively). Subjects not fulfilling the inclusion criteria or meeting any of the exclusion criteria will be recorded as screening failures;
- Study restrictions: study restriction criteria will be checked, according to [Section 7.2](#);
- ACQ-5: asthma control level will be re-assessed using the ACQ-5, according to [Section 7.3.6.1](#);
- Randomisation: subjects will be randomised according to [Section 6.5](#).
- Concomitant medications: concomitant medications taken by the subject since the screening visit and during TP1 will be checked and recorded;
- AE recording: the status of AEs ongoing at the screening visit will be checked and updated in the eCRF when applicable. Any new AE occurring since the previous visit will be checked and recorded in the eCRF, as well as the related concomitant medications. Any AE occurring during the study visit must also be monitored and recorded in the eCRF;
- Pregnancy test: urine samples will be collected from childbearing potential female subjects for pregnancy testing, according to [Section 7.3.5](#);
- Physical examination: a full physical examination will be performed, and any new CS abnormality revealed since the screening visit will be recorded as an AE;
- 12-lead ECG: a single ECG will be recorded to assess ECG parameters (HR, PR, QRS and QTcF), according to [Section 7.3.3](#). The assessment will be performed in pre-dose: within 1 h before T0; and in post-dose: 45 min, 1 h 45 min and 2 h 45 min after T1;
- Blood pressure: SBP and DBP will be measured after 5 min in supine position, as described in [Section 7.3.2](#). The assessment will be performed before or after the 12-lead ECG assessment, in pre-dose: within 1 h before T0; and in post-dose: 45 min, 1 h 45 min and 2 h 45 mins after T1;
- Lung function: serial spirometries will be performed according to [Section 7.3.1](#). Spirometry assessments will be collected in pre-dose: 45 min and 15 min before T0; and in post-dose: 5 min, 15 min, 30 min, 1 h, 1 h 30 min and 3 h after T1;
- Study treatment administration: single-dose (██████████) treatment administration according to [Section 6.2.3](#), based on each subject's randomisation arm;
- ██████████

TP1 will be followed by a 2- to 7-day wash-out period from the propellant.

#### 7.1.4 Treatment Period 2 (TP2)

TP2 is the second visit of the investigational phase. It takes place 2 to 7 days after TP1.

The following procedures and assessments will take place during this ambulatory visit:

|  |                      |
|--|----------------------|
| Clinical Study Code No.: CLI-05993AB6-07 | Version No.: 2.0     |
| EUDRACT No.: 2022-000536-36              | Date: 30 August 2022 |

- Study restrictions: study restriction criteria will be checked, according to [Section 7.2](#);
- Concomitant medications: concomitant medications taken by the subject since TP1 and during TP2 will be checked and recorded;
- AE recording: the status of AEs ongoing at TP1 will be checked and updated in the eCRF when applicable. Any new AE occurring since the previous visit will be checked and recorded in the eCRF, as well as the related concomitant medications. Any AE occurring during the study visit must also be monitored and recorded in the eCRF;
- Pregnancy test: urine samples will be collected from childbearing potential female subjects for pregnancy testing, according to [Section 7.3.5](#);
- Physical examination: a full physical examination will be performed and any new CS abnormality revealed since TP1 will be recorded as an AE;
- 12-lead ECG: a single ECG will be recorded to assess ECG parameters (HR, PR, QRS and QTcF), according to [Section 7.3.3](#). The assessment will be performed in pre-dose: within 1 h before T0; and in post-dose: 45 min, 1 h 45 min and 2 h 45 min after T1;
- Blood pressure: SBP and DBP will be measured after 5 min in supine position, as described in [Section 7.3.2](#). The assessment will be performed before or after the 12-lead ECG assessment, in pre-dose: within 1 h before T0; and in post-dose: 45 min, 1 h 45 min and 2 h 45 min after T1;
- Lung function: serial spirometries will be performed according to [Section 7.3.1](#). For each subject, the assessments will start at approximately the same time of the day as at TP1. Spirometry assessments will be collected in pre-dose: 45 min and 15 min before T0; and in post-dose: 5 min, 15 min, 30 min, 1 h, 1 h 30 min and 3 h after T1;
- Study treatment administration: single-dose (██████████) administration of the second propellant (based on each subject's randomisation arm, following a cross-over design), according to [Section 6.2.3](#). For each subject, treatment administration will start at approximately the same time of the day as at TP1;
- ██████████

A follow-up call (or visit, if deemed necessary by the Investigator) will be performed 7 to 10 days after TP2.

### 7.1.5 Follow-up Call

A follow-up call (or visit, if deemed necessary by the Investigator) will be performed 7 to 10 days after TP2, for a safety follow-up.

The following assessments will be performed during this call:

- AE recording: the status of any AEs ongoing at TP2 will be checked and updated in the eCRF, along with the related concomitant medications. Any new AE occurring since TP2 will be checked and recorded in the eCRF, as well as the related concomitant medications;

|  |                      |
|--|----------------------|
| Clinical Study Code No.: CLI-05993AB6-07 | Version No.: 2.0     |
| EUDRACT No.: 2022-000536-36              | Date: 30 August 2022 |

- Concomitant medications: concomitant medications taken by the subject since TP2 will be checked and recorded.

### 7.1.6 Early Termination Visit

In the case of early discontinuation, an Early Termination visit will be performed in order to assess the subject's safety.

The following assessments will be performed:

- Concomitant medications: concomitant medications taken by the subject since the last study visit and during the Early Termination visit will be checked and recorded;
- AE recording: the status of any AEs ongoing at the previous visit will be checked and updated in the eCRF, along with the related concomitant medications. Any new AE occurring since the previous visit will be checked and recorded in the eCRF, as well as the related concomitant medications. Any AE occurring during the study visit must also be monitored and recorded in the eCRF;
- Pregnancy test: urine samples will be collected from childbearing potential female subjects for pregnancy testing, according to [Section 7.3.5](#);
- Physical examination: a full physical examination will be performed and any new CS abnormality revealed since the previous visit will be recorded as an AE;
- 12-lead ECG: a single ECG will be recorded to assess ECG parameters (HR, PR, QRS and QTcF), according to [Section 7.3.3](#);
- Blood pressure: SBP and DBP will be measured after 5 min in supine position, as described in [Section 7.3.2](#).

### 7.2 Study Restrictions and Standardisation

The following restrictions should be applied and should be checked at each visit at the investigational site:

- No smoking or intake of substances containing nicotine: up to the end of the investigational phase (for the eligibility of ex-smokers, see Exclusion criterion #9, [Section 4.3](#));
- Current asthma therapy: low-dose ICS-formoterol, SABA, or low-dose ICS (whenever SABA is taken) should be taken as needed, but not more than twice a week (2 events) in the 4 weeks prior to screening or in the 6 weeks prior to randomisation, and between the treatment periods.

A definition of low-dose ICS is provided in Inclusion criterion #6, [Section 4.2](#).

The following restrictions should be applied before spirometry assessments (i.e. before screening, TP1 and TP2) [\[16\]](#):

- Wash-out period:
  - Inhaled/nebulised SABA: 6 h;
  - ICS (in combination with SABA): 24 h;
  - ICS-formoterol: 24 h.

|  |                      |
|--|----------------------|
| Clinical Study Code No.: CLI-05993AB6-07 | Version No.: 2.0     |
| EUDRACT No.: 2022-000536-36              | Date: 30 August 2022 |

- No intake of intoxicants such as alcohol, caffeine/xanthine containing beverages or food (coffee, tea, chocolate, cola) within 8 h. Decaffeinated products are permitted;
- No strenuous activities within 1 h;
- Avoiding wearing clothes that substantially restrict full chest and abdominal expansion.

### 7.3 Investigations

#### 7.3.1 Lung Function Assessment

Lung function will be evaluated at the timepoints specified in [Table 1](#).

Centralised spirometry will be used for the assessment performed during TP1 and TP2 for this trial while the local spirometer is used for the eligibility lung function assessments. The specific procedures for centralised spirometry will be provided to the Investigator by the centralised spirometry company.

Calibration of the local spirometer must be performed at each screening visit prior to spirometry manoeuvres and the reports must be kept at the investigational sites and be accessible to the clinical research associate and the Sponsor. Personnel using the spirometer will be adequately trained to follow the commonly accepted procedures. The predicted values will be calculated according to the formulas reported by Quanjer et al. [\[17\]](#).

The same brand and model of spirometer will be provided by the centralised spirometry company for all measurements during TP1 and TP2 and adjusted for the ATS/ERS standards [\[16\]](#). The predicted values will be calculated according to the formulas reported by Quanjer et al. [\[17\]](#). Personnel using the spirometer will be adequately trained to follow the commonly accepted procedures. The spirometer provided by the centralized spirometry company do not need the calibration procedure.

Subjects should be at rest before each lung function test. All measurements are to be made with the subjects in sitting or standing position (for the same subject, the position must be consistent throughout the study) with the nose clipped. Values will be corrected for body temperature and pressure saturation (BTPS) conditions [\[18\]](#).

At each timepoint specified in [Table 1](#), subjects will perform three attempts for the measurement of FEV1 and peak expiratory flow (PEF). In order to be considered as technically satisfactory attempts, measurements should be free from cough and false-start. The highest value (in L) of FEV1 and PEF from three technically satisfactory attempts (not necessarily coming from the same curve) will be recorded. The two largest FEV1 measurements must be within 150 mL of each other (or 100 mL, if the forced vital capacity [FVC] value is  $\leq 1$  L). If the difference is larger, additional spirometry assessments (up to 8) will be made until the above criterion is met. If, at the end, the tests are not within 150 mL, the highest value of FEV1 and PEF will be recorded and used for eligibility or continuation criteria.

In case lung function measurements obtained at screening were below the expected value, (see Inclusion criterion #4 in [Section 4.2](#)), the subject will be asked to return to the investigational site once before randomisation to repeat the test. If, at that time, FEV1  $\geq 60\%$  of the predicted normal value and  $\geq 1.5$  L, the subject can be included in the study. Otherwise, the subject will be discharged and recorded as a screening failure.

If a subject shows a progressive reduction in FEV1 with each subsequent blow, with cumulative drop above 15% of the starting value, the test procedure may be terminated in the interest of the subject's safety. During the 3 h post-dose serial spirometry, the use of rescue medication should

|  |                      |
|--|----------------------|
| Clinical Study Code No.: CLI-05993AB6-07 | Version No.: 2.0     |
| EUDRACT No.: 2022-000536-36              | Date: 30 August 2022 |

be as limited as possible and rescue medication intake must be under medical control. The serial spirometries can be discontinued after the intake of rescue medication, based on the Investigator's judgement. In this case and if deemed necessary, a safety spirometry can be performed by the site. Details on intake of rescue medication during the treatment periods will be recorded in the eCRF.

The restrictions to be applied before spirometry assessments are described in [Section 7.2, \[16\]](#). In case any of the restrictions is not respected, the study visit should be rescheduled once, to be performed within the allowed time window between the previous and the current visit.

For the post-dose lung function assessments, the following time deviations from the theoretical post-T1 times will be allowed (actual time to be recorded is the time when the first lung function manoeuvre starts):

- 5 min and 15 min post-dose:  $\pm 2$  min;
- 30 min and 1 h post-dose:  $\pm 5$  min;
- 1h 30 min and 3 h post-dose:  $\pm 15$  min.

Longer time deviations will be evaluated on a case-by-case basis during the Blind Data Review meeting.

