### 12.3.2 Missing Data

As a general rule, missing data will not be imputed.

For serial spirometry-derived parameters, the following rules will apply:

- Pre-dose FEV1 and PEF:
  - In case only one pre-dose measurement is available, it will be used as pre-dose FEV1 and PEF;
  - In case no pre-dose measurements are available, the pre-dose FEV1 and PEF will be considered missing.
- FEV1 AUC0-3h calculation:
  - In case only one pre-dose measurement is available, it will be used as pre-dose value (corresponding to time 0 for the calculation of the area under the concentration-time curve [AUC]);
  - In case no pre-dose measurements are available, the entire curve will be considered missing;
  - Single, isolated missing values (different from pre-dose) will be replaced by linear interpolation using adjacent values;
  - In case of two or more consecutive missing timepoints, the entire curve will be considered missing;
  - In case of three or more missing timepoints, the entire curve will be considered missing.

Further details on dealing with missing data, along with the handling of possible outliers, will be described in the SAP. Other critical missing data, if any, will be discussed during the review of the data. Decisions will be fully documented in the Data Review Report.

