5. GENERAL METHODOLOGY

5.1 ANALYSIS SETS

5.1.1 *Analysis sets*

The following analysis sets will be considered in the statistical analysis:

Enrolled Set (ENR): subjects who *signed an informed consent* to participate in this study

Randomised Set (RND): subjects who were *randomised* into this study

Safety Set (SAF): subjects who were randomised and *received at least one dose of study drug*

Per Protocol (PP) Analysis Set: subjects from the SAF, excluding the subjects having important protocol deviations impacting the analysis set

Notes:

- Having signed an informed consent is defined as having a complete informed consent signature date in the database.
- Randomised is defined as having a randomisation date in the database or any information to confirm randomisation.
- Having received at least one dose of study drug is defined as having an exposure date or any information confirming exposure.
- Exact definition of important protocol deviations concerning PP will be discussed by the clinical team and described in the DRR. The subjects to be excluded from PP analysis set will be defined in the DRR.

Unless stated otherwise, the SAF will be used for the general characteristics, safety [REDACTED] tables, listings and figures. The variables assessing the primary study objective will also be analysed considering the PP, for sensitivity purposes.

Since a cross-over design will be used, the inclusion in the analysis sets will be defined at subject level on a per-period basis and at subject level overall (in case all periods are affected). In case of important protocol deviations impacting specific time points, only the affected data at the specific time point will be excluded from the applicable analysis sets. These cases will be documented in the DRR.

5.1.2 *As planned versus as actual analysis*

For analyses done on the safety analysis set and on PP analysis set (excluding general characteristics analyses), the actual treatment of the subject will be considered. In addition, the actual treatment will be presented in all listings.

For all other analyses, the planned treatment (sequence) will be used.

	Statistical Analysis Plan	
CLI-05993AB6-07		Final 1.0 of 22DEC2022

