- Unscheduled visits will be presented as 'Unscheduled' unless the decision to reallocate the visit is fully documented in the DRR. In case of reallocation, the unscheduled visit will be presented with the same label as the replaced planned visit (see rules above)
- Other visits not covered by the rules above will be presented using similar labels to the ones used in SDTM (XX.VISIT)

The analysis time point labels for spirometry, vital signs and ECG parameters, will be assigned using the following time windowing rules.

Next to the screening value, all assessments, including unscheduled assessments, will be allocated to analysis windows. Tables will present the analysis windows as defined below and listings will present the analysis windows, as well as the CRF visits.

Allocation of assessments will be done according to the following tables:

Spirometry:

Analysis time point window	Target time from dose of study drug per period (minutes)	Time interval (minutes)
45min Pre-dose	<0	Day 1, before study drug
15min Pre-dose	<0	Day 1, before study drug
5min	5	[3 ; 10)
15min	15	[10 ; 23)
30min	30	[23 ; 45)
1h	60	[45 ; 75)
1.5h	90	[75 ; 135)
3h	180	[135 ; 240]

Notes:

- Target time and time interval will be calculated in each treatment period from the first inhalation for pre-dose assessments and from the last inhalation for post-dose assessments.
- The 45min pre-dose and 15min pre-dose assessments will first be allocated to analysis windows before calculation of the pre-dose mean value.

	Statistical Analysis Plan	
CLI-05993AB6-07		Final 1.0 of 22DEC2022

Vital signs and ECG:

Analysis time point window	Target time from dose of study drug per period (minutes)	Time interval (minutes)
Pre-dose	<0	Day 1, before study drug
45min	45	[15 ; 75)
1h 45min	105	[75 ; 135)
2h 45min	165	[135 ; 240]

Note: Target time and time interval will be calculated in each treatment period from the first inhalation for pre-dose assessments and from the last inhalation for post-dose assessments.

Per parameter and analysis window, the value closest to the target time will be used in analysis tables and figures, other values will only be listed. If more than one value is located at the same distance from the target, then the latest in time will be selected. The value latest in time will be identified using, in order of preference, the assessment time, the visit and time point label or the group identifier. Missing values are removed before the selection is made.

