5.3 IMPUTATION AND ROUNDING RULES

5.3.1 *Missing values*

[figure not shown]
No imputation of missing values will be done (i.e. observed cases analysis).

5.3.2 *Handling partially or completely missing dates in calculations*

In case of missing date(time)s for FEV₁ assessments, needed for the calculation of AUC_{0-3h}, these cases will be discussed and documented in the DRR.

Partially missing date of first diagnosis event will be imputed as follows for the calculation of time since event:

- Missing day will be imputed with the first day of the month
- Missing day and month will be imputed with 1st JAN

	Statistical Analysis Plan	
CLI-05993AB6-07		Final 1.0 of 22DEC2022

Partially missing date of most recent exacerbation event will be imputed as follows for the calculation of time since event:

- Missing day will be imputed with the last day of the given month
- Missing day and month will be imputed with 31st DEC

5.3.3 *Values below or above a threshold*

Safety values expressed as below (or above) the limit of quantification will be imputed by the value of the quantification limit itself. Listings will always show the non-imputed values.

5.3.4 *Rounding of derived variables*

Derived variables will be rounded at display level:

- AE duration will be presented with 1 decimal.
- Mean of duplicates (blood pressure)/triplicates (ECG) will be rounded to the nearest integer.
Note: since the rounding is applied at display level, in the listings, the change from baseline could be slightly different to the listed value at time point t – baseline value
- Mean of duplicates (lung function) will be rounded to same number of decimal places as the individual values.
Note: since the rounding is applied at display level, in the listings, the change from baseline could be slightly different to the listed value at time point t – baseline value
- FEV₁ AUC_{0-3h} will be rounded to the same number of decimal places as the actual FEV₁ values.
- Relative change from baseline will be presented with 1 decimal.
- Time since first diagnosis and most recent exacerbation will be presented with 1 decimal.

5.3.5 *Outliers*

Potential outliers will be discussed during the review of the data by the Chiesi team. Decisions on whether values are to be excluded from the analysis will be fully documented in the DRR.

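### Rescue bronchodilator taken before the 15 min reading has no rule in the primary FEV1 analysis, and both default outcomes can move the estimate towards equivalence

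*Protocol*

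**What the plan says.** Protocol 7.3.1 asks that rescue during the 3 h of post-dose spirometry be kept to a minimum, and "rescue medication intake must be under medical control". It does not forbid it. Afterwards, "The serial spirometries can be discontinued after the intake of rescue medication", at the investigator's discretion, and the site may perform a safety spirometry.

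Four sets of rules then decide what reaches the primary analysis:

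- **Missing values.** Protocol 12.3.2: "As a general rule, missing data will not be imputed". SAP 5.3.1: "No imputation of missing values will be done (i.e. observed cases analysis". The further SAP detail for spirometry concerns pre-dose values and the AUC, not the 15 min value.
- **Choice of reading.** SAP 5.2.4: "all assessments, including unscheduled assessments, will be allocated to analysis windows". The 15 min window is [10 ; 23) min after the last inhalation, and "the value closest to the target time will be used in analysis tables and figures, other values will only be listed". Rescue plays no part.
- **Model.** SAP 2.5.3 and the code in SAP 9.1 fit treatment, subject and period as fixed effects, with the period baseline as covariate.
- **Rescue data.** SAP 2.6 summarises users and puffs by treatment. It does not link them to FEV1.

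**The concern.** Protocol 1.2 explains why the trial exists: the CHMP considered that bronchoconstriction from HFA-152a could have gone unseen because the propellant had been given with bronchodilators. A subject who reacts and is rescued before the 15 min reading is the case the trial looks for. For that subject the primary variable either contains a bronchodilator effect or is absent.

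If the reaction was to HFA-152a, both outcomes shrink the estimated difference. If it was to HFA-134a, the reference looks better than it is. The window for this is longer than 15 minutes: dosing may take 12 min and the reading may be 2 min late, so up to 12 + 15 + 2 = 29 min can pass between first inhalation and reading.

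**Working it through.** **1. The plan's own figure.** Inputs from protocol 12.1 and SAP 1.3: margin ±10, within-subject SD 8, 95% CI, 95% power, 20 evaluable, 16% non-evaluable.

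- Normal approximation, true difference 0: n = 2 × [8 × (1.96 + 1.96)/10]² = 2 × 3.136² = 19.67, so 20.
- SE = 8 × √(2/20) = 2.530. Power = 2Φ(10/2.530 − 1.96) − 1 = 0.954.
- 20/0.84 = 23.8, so 24 randomised.

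The stated size reproduces. With the t distribution, power is 0.92 at n = 20 and 0.97 at n = 24. These are the reference values below.

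**2. Does one missing period remove the subject?** The SAP model was fitted to one simulated data set of 20 subjects. Deleting one subject's HFA-152a value gave a treatment estimate of −0.2298 (SE 2.597). Deleting that subject altogether gave the same estimate and SE.

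**3. Shift in the estimate.** The documents give no frequency or size of reaction, so these are assumptions: k subjects fall D points of baseline further on HFA-152a at 15 min, and the others show no difference. The true mean difference is −kD/n. One lost reactor among 24 hides D/24, which is 15/24 = 0.63 to 30/24 = 1.25 points for D = 15 to 30. For n = 24, k = 3, D = 30, all rescued early:

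- true values kept: 3 × 30/24 = 3.75 points;
- periods lost: 0;
- bronchodilated: inclusion criterion 5 puts a positive salbutamol response at more than 12% of the pre-bronchodilator FEV1. After a 30% fall that is 0.12 × 70 = 8.4 points, leaving 21.6, so 3 × 21.6/24 = 2.70;
- proposed fix, assuming the pre-rescue reading shows 80% of the fall: 3 × 24/24 = 3.00.

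**4. Chance that the 95% CI lies within ±10.** Simulation of the 2×2 cross-over: 50,000 trials per cell, SD 8, subject and period fitted, no baseline covariate, reactors placed at random over sequences, all k rescued early.

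| n | k | D | true value | period lost | with fix |
|---|---|---|---|---|---|
| 24 | 1 | 20 | 0.95 | 0.96 | 0.96 |
| 24 | 2 | 20 | 0.89 | 0.95 | 0.92 |
| 24 | 2 | 30 | 0.74 | 0.95 | 0.84 |
| 24 | 3 | 30 | 0.48 | 0.94 | 0.68 |
| 20 | 2 | 20 | 0.76 | 0.88 | 0.82 |
| 20 | 3 | 30 | 0.25 | 0.85 | 0.46 |

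For the bronchodilated outcome with the 8.4-point response at n = 24, D = 30, the chance is 0.87 for k = 2 and 0.75 for k = 3. For k = 1, D = 20, no outcome exceeds 0.97. If only one of three reactors (n = 24, D = 30) is rescued early, the figures are 0.48 true, 0.69 with the period lost and 0.55 with the fix.

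**The case against.** **Data review could deal with it.** Protocol 12.3.2 sends other critical missing data to the data review, SAP 5.2.4 has unscheduled readings checked before database lock, and SAP 5.3.5 covers outliers. Protocol 5.2 requires 6 h without SABA before any spirometric assessment. Read literally, that makes a post-rescue reading a deviation, for which SAP 5.1.1 says "only the affected data at the specific time point will be excluded from the applicable analysis sets". Protocol 7.2 supports a narrower reading, that the wash-out applies before the visits. These safeguards are real, but none states a rescue rule, and exclusion only turns a bronchodilated value into a missing one. Whether a site's safety spirometry would reach the analysis data, which come from centralised spirometry, is not stated.

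**It will be rare, and reactors will be seen.** Subjects are GINA Step 1 with ACQ-5 below 1.5, and rescue is discouraged, so the event is probably uncommon. Reactors remain visible in the adverse event and rescue tables, in the table of falls above 15% if the fall was recorded, and in the 5 min ANCOVA if rescue followed that reading. This stands, and it lowers the severity. It does not correct the 15 min estimate, for which the margin and sample size were set.

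**The remedy is a choice of estimand.** This is partly fair. A pre-rescue value can err either way. In the bronchodilated case it gains little at the assumed response: 0.75 becomes 0.68, and 0.87 becomes 0.84, for three and two reactors with D = 30 at n = 24.

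**Readings that go too far.** A reader might take the sentence "with cumulative drop above 15% of the starting value, the test procedure may be terminated" as a rescue trigger. It concerns decline from blow to blow within one test and does not mention rescue. A reader might also treat the 12% in inclusion criterion 5 as 12 points of pre-dose baseline. After a 20% or 30% fall it is 9.6 or 8.4 points, and subjects may qualify on a challenge test alone.

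**Conclusion.** The gap is real and narrow. It concerns only rescue during dosing or before the 15 min reading; subjects rescued later keep a valid primary value. For those affected, the stated rules yield a missing or a bronchodilated FEV1, and if HFA-152a is the cause both favour equivalence.

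At n = 24, one reactor with a 20-point fall makes no material difference (0.95 against 0.96 to 0.97). Two or three strong, early-rescued reactors can change the conclusion. The sizes rest on assumed k, D, bronchodilator response and 80% carry, none of which the documents supply, and on a model without the baseline covariate.

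A reader might infer that the trial cannot detect bronchoconstriction, or that reactors vanish from the report. The documents support neither: the other planned analyses would still show them. If nobody takes rescue before 15 min, there is no effect. Severity is low to moderate.

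**What to change.** Rescue must never be delayed or restricted.

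- **Protocol 7.3.1:** where safe and without delaying rescue, measure FEV1 immediately before rescue and record the time.
- **SAP 2.5.2:** do not use an FEV1 taken after rescue as the 15 min value in the primary analysis. Use the last post-dose FEV1 before rescue. If there is none, the value stays missing and the ANCOVA is repeated with assumed falls, for example −15% to −30%, labelled as assumptions.
- **Sensitivity analysis:** keep the present observed-case ANCOVA.
- **Protocol 12.3.2 and SAP 5.3.1:** add a matching exception to the no-imputation rule.

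The cost is one protocol sentence, two short exceptions, one derivation rule and two sensitivity runs, all settled before unblinding. Rescue times and puffs are already collected (SAP 2.6.1). The downside is that the pre-rescue value may overstate a fall that would have resolved or understate one still deepening, and a subject rescued with no earlier reading stays missing. The change reduces the bias without removing it.
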